Hysterosalpingo-contrast sonography (HyCoSy) was introduced as a safer and less-painful alternative to HSG with comparable diagnostic accuracy and superiority in diagnosing uterine, ovarian, and myometrial pathologies.(1,6,9,10-12) HyCoSy is the recommended tubal test by NICE for women not known to have tubal disease, as an alternative to HSG, whenever appropriate expertise is available.(3) Air and saline use as contrast medium with HyCoSy made the procedure highly operator dependent.(1,6,13-16) Hyperechogenic and longer-lasting echogenic media then followed but are currently commercially unavailable or not approved for tubal testing.(1,6,14– 19)

In 2007, ExEm gel (GynaecologIQ, Delft, Netherlands) was introduced(20) and registered as European Confirmatory (CE) approved drug for tubal testing.(15) Hysterosalpingo-foam sonography (HyFoSy), using diluted ExEm gel foam, has been established as a safe, feasible, tolerable, and accurate alternative to HyCoSy and HSG that has been widely used in infertility clinics.(1,6,7,9,10,14,18,19,21–26)

In 2017, hysterosalpingo-lidocaine-foam sonography combined with power doppler (HyLiFoSy-PD) was introduced as a cost effective and less painful possible alternative to HyFoSy that can be used whenever the contrast media is unavailable. "Flaming tube" sign, detected using power doppler (PD), was also described as to allow easier recognition of tubal patency.(27) Our study aims to compare the diagnostic accuracy of HyLiFoSy-PD with the most commonly used tubal test; HSG, with reference to the gold standard tubal test; laparoscopy and dye testing.

5. Objective:

The aim of this study is to evaluate the difference between the diagnostic accuracy of Hysterosalpingo-lidocaine-foam sonography and hysterosalpingography, with reference to the gold standard tubal test; laparoscopy with dye testing.

6. Study Design:

This will be a cross-sectional study

7. Scientific committee approval:

8. Study methodology:

Population of study, disease condition and setting:

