- 12.Patients will be asked about the degree of discomfort or pain they felt during and immediately after the procedure. Using categorical verbal rating scale (VRS),(28) Procedure will be stopped if a patient experiences severe pain.
- 13.Patients will be followed up overnight and monitored for any other procedure-related side effects or complications.
- 14. Within a week following the HyLiFoSy-PD procedure, standard LDT will be carried out by experienced endoscopists who will be blinded to the results of HyLiFoSy-PD. During LDT, tubal patency will be tested using methylene blue dye. Tubal evaluation during LDT will be classified as: patent with immediate spill, patent with delayed spill, or blocked.

Possible Risk (mention if there is any risk or not)

Side effects such as vasovagal reactions, allergic reaction, and venous intravasation have been reported in literature in hysterosalpingo-foam studies. However, in our previous hysterosalpingo-lidocaine-foam sonography study, none of these side effects were encountered. For the possible risk of infection, all patients will be given prophylactic antibiotics. In addition, any case with visible hydrosalpinx or signs or symptoms of PID on US prior to performing HyLiFoSy-PD will not perform the procedure.

9. Study outcomes:

Primary outcomes

1. Diagnostic accuracy of HyLiFoSy and HSG with reference to LDT, in terms of sensitivity, specificity, positive predictive value, negative predictive value, and overall accuracy.

Secondary outcome parameters

1 -Diagnostic accuracy of adding power doppler to the HyLiFoSy.

2-Evaluate the procedure associated pain

3-Evaluate the procedure duration

4-Percentage of failed or inconclusive attempts and possible reasons for

that

5-Incidence and rate of potential complications for example: vasovagal and allergic reactions, venous intravasation.

10. Sample size: Using the following equation:(29)

$$N_{\text{Disease}} = \frac{\left\{z_{1-\alpha/2}\Lambda + z_{1-\beta}\sqrt{\Lambda^2 - \zeta^2(3+\Lambda)/4}\right\}^2}{\Lambda\zeta^2}$$

where $\Lambda = (1 - Se_1)Se_2 + (1 - Se_2)Se_1$ and $\zeta = (1 - Se_1)Se_2 - (1 - Se_2)Se_1$.

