With power of the study 90%, CI 95%, average sensitivity of HSG is 0.55,(4) and sensitivity of HyLiFoSy-PD is 90%,(30), prevalence of tubal pathology is 30%,(1); 100 patients are required to fulfill the sample size. To compensate for any possible dropouts (5%), 5 more patients will be recruited. So, the total sample size will be 105.

11. Statistical analysis:

After recording and collecting the data, statistical analysis will be performed using the Statistical Package for the Social Sciences (SPSS, version 16.0, SPSS Inc, Chicago, Illinois, USA). Data will be statistically described in terms of mean and standard deviation if they were of normal distribution, and in terms of median and range if they were not normally distributed. Frequencies (number of cases) and percentages will be used when appropriate. Accuracy will be represented using the terms sensitivity, specificity, PPV, NPV, and overall accuracy. Testing the difference in the results of tests was done using

one-way analysis of variance (ANOVA) test. P-values less than 0.05 will be considered statistically significant.

12. Source of funding:

Self-funding

13.Time plan From 1/6/2022 – 1/6/2024 (2 years)

14.References:

- Optimal evaluation of the infertile female. Fertility and Sterility. 2006 Nov;86(5 SUPPL.).
- Fertility problems: assessment and treatment Clinical guideline [Internet]. 2013. Available from: www.nice.org.uk/guidance/cg156
- 5. Tsiami A, Chaimani A, Mavridis D, Siskou M, Assimakopoulos E, Sotiriadis A. Surgical treatment for hydrosalpinx prior to in-vitro

KASR ALAINY

Cairo University

fertilization embryo transfer: a network meta-analysis. Ultrasound Obstet Gynecol. 2016 Oct 1;48(4):434–45.

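### The primary outcome is five unranked accuracy measures with no decision rule and no planned confidence intervals, although only sensitivity is powered

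*Combined protocol and SAP*

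**What the plan says.** - **Objective (section 5).** The aim is comparative: to "evaluate the difference between the diagnostic accuracy of Hysterosalpingo-lidocaine-foam sonography and hysterosalpingography", with laparoscopy and dye testing (LDT) as reference.
- **Primary outcome (section 9).** There is one numbered item, the accuracy of HyLiFoSy and of HSG, "in terms of sensitivity, specificity, positive predictive value, negative predictive value, and overall accuracy". The five are not ranked. The effect of adding power Doppler is a separate, secondary outcome.
- **Sample size (section 10).** A paired-sensitivity formula is used, with these inputs: "With power of the study 90%, CI 95%, average sensitivity of HSG is 0.55", "sensitivity of HyLiFoSy-PD is 90" per cent, and "prevalence of tubal pathology is 30" per cent. The result is that "100 patients are required to fulfill the sample size", raised to 105 for dropout. No specificity, predictive value or overall accuracy enters.
- **Analysis (section 11).** "Accuracy will be represented using the terms sensitivity, specificity, PPV, NPV, and overall accuracy". One procedure, a one-way ANOVA, is named for comparing the tests and is not tied to any measure. Then: "P-values less than 0.05 will be considered statistically significant". There is no multiplicity rule. A 95% confidence level appears only as a sample-size input in section 10, and no interval is planned for any measure or difference.

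**The concern.** The plan asks whether two tests differ in accuracy, but does not say which of five measures answers the question. Three things follow.

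1. The measure that carries the conclusion can be settled after the results are seen, and the single 0.05 threshold does not allow for that choice.
2. Sensitivity and specificity can move in opposite directions. Section 4 treats both kinds of error as harmful: falsely occluded tubes can lead to unneeded interventions, and falsely patent tubes to failed IVF. Nothing says what is concluded if one improves and the other worsens.
3. About 30 women are expected to be LDT-positive. With that number, a percentage and a p-value do not show how imprecise the estimate is. A non-significant specificity result could also be misread as showing that the tests are equally specific.

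**Working it through.** **1. The plan's own figure.** Inputs from section 10: Se₁ = 0.55, Se₂ = 0.90, two-sided α = 0.05 (the formula uses z at 1−α/2), power 90%, prevalence 30%.

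- Λ = 0.45 × 0.90 + 0.10 × 0.55 = 0.405 + 0.055 = 0.46
- ζ = 0.405 − 0.055 = 0.35, so ζ² = 0.1225
- √(Λ² − ζ²(3+Λ)/4) = √(0.2116 − 0.1060) = 0.325
- N(diseased) = (1.960 × 0.46 + 1.282 × 0.325)² / (0.46 × 0.1225) = 1.737 / 0.05635 = 30.8
- Total = 30.8 / 0.30 = 102.8, so 103 (104 if 30.8 is first rounded up to 31)

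This agrees with the stated 100 to within 3%. With exactly 30 diseased women the same formula gives 89% power. The size is therefore sound for sensitivity, and it rests on sensitivity only.

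**2. Power for specificity.** About 70 women would be LDT-negative. Section 4 gives HSG specificity as 87%. The documents give no specificity for HyLiFoSy, so a range is assumed. The same formula with n = 70 gives:

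| Assumed HyLiFoSy specificity | Power |
|---|---|
| 0.92 | 15% |
| 0.95 | 36% |
| 0.97 | 59% |
| 0.99 | 88% |

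**3. False-positive rate if every measure is compared at 0.05.** Assumptions: 20,000 simulated trials, 100 women, 30% prevalence, both tests with sensitivity 0.70 and specificity 0.87, results independent given LDT status. Mid-p McNemar is used for sensitivity, specificity and overall accuracy, and two-proportion z tests for PPV and NPV.

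| Event | Two-sided | In favour of HyLiFoSy |
|---|---|---|
| Sensitivity alone p < 0.05 | about 4% | about 2% |
| Sensitivity or specificity | about 8.4% | – |
| Any of the five | about 10% | about 5% |

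With these tests PPV and NPV add almost nothing. The excess comes from sensitivity, specificity and overall accuracy.

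The figure depends on the tests chosen:

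- Exact McNemar on sensitivity, specificity and overall accuracy gives about 6.6% for any of the three. That test is conservative, so its rate for sensitivity alone is also lower, and 6.6% should not be set against the 4% above.
- Large-sample McNemar with generalised score tests for PPV and NPV, at 0.55/0.87, gives about 12%.

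**4. Can the choice of measure change the answer?** Take sensitivity 0.55 versus 0.90 and specificity 0.87 versus 0.95 (the last value assumed), with the large-sample McNemar and score tests. About 10% of simulated trials then show no significant sensitivity gain but a significant gain on another measure.

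**5. Precision.** The expected number of LDT-positive women is 100 × 0.30 = 30. If 27 of 30 were detected (90%, the planning value), the exact 95% interval is 73% to 98%, and the Wilson interval is 74% to 97%. This is an illustration on a per-woman basis. Section 8 observes each tube, and section 11 does not state the unit of analysis.

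**The case against.** The strongest reply is that the plan does not set out five tests. Section 9 has one primary item described by five summaries of the same tables, section 11 uses descriptive wording for them, and the only comparison named is one ANOVA attached to no measure. This stands. It is an inference, not a stated rule, that each measure is judged separately at 0.05. The 10% is conditional on that reading and on tests the plan does not name. A one-way ANOVA does not suit paired yes/no results, so the error rate of the plan as written cannot be calculated. But the reply does not remove the gap: the objective is a difference, one threshold covers every p-value, and nothing says which measure decides.

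A reader might also infer that the trial is set up to claim superiority of HyLiFoSy. The documents do not support that. They speak of evaluating a difference and state no success criterion.

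Nor does the familiar figure for five independent tests, 1 − 0.95⁵ = 22.6%, apply. All five measures come from the same women and the same tables, so they are correlated.

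Finally, reporting all five is normal in a diagnostic study, and a fixed testing order is one acceptable solution among several. Both points are fair. The proposal below keeps all five and only ranks them.

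**Conclusion.** The point holds as an inexpensive improvement to the plan. The documents themselves show five unranked primary measures, a sample size that rests on sensitivity alone, one blanket significance threshold and no planned intervals. The size of the consequence rests on assumptions: if each measure is compared at 0.05, about 10% two-sided against about 4% for sensitivity alone, and about 5% against 2% in favour of HyLiFoSy. Under the alternative tests and accuracy values tried, the any-measure rate ran from about 6.6% to 12%. The 10% should not be read as the chance of wrongly declaring HyLiFoSy better, because it counts differences in both directions. The lack of intervals matters whichever tests are used.

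A related inconsistency affects any repair. The primary outcome names HyLiFoSy, with power Doppler as a secondary addition, whereas the sensitivity used for the sample size is that of HyLiFoSy-PD. Even the powered measure is therefore not clearly that of the primary index test.

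**What to change.** In sections 9 and 11:

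1. **Primary.** Name the paired difference in sensitivity, index test minus HSG in LDT-positive women, as the single primary comparison. Use McNemar's test and give a 95% confidence interval for the difference.
2. **Index test.** State whether it is HyLiFoSy or HyLiFoSy-PD, and make sections 9 and 10 agree.
3. **Key secondary.** Name the paired difference in specificity with its 95% interval, tested only if sensitivity is significant. Always report it beside sensitivity, and state that a gain in sensitivity will not be called better overall accuracy if specificity falls.
4. **Descriptive.** Report PPV, NPV and overall accuracy with 95% intervals (exact or Wilson) and no significance claim.

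The cost is a few sentences and the interval output. No more patients are needed, because the primary comparison becomes the one the study is sized on. Keeping several primaries with a Bonferroni correction would not be free. By the plan's formula, powering sensitivity at 0.025 (two primaries) needs 38 diseased women, 38/0.30 ≈ 127 in total. At 0.01 (five primaries) it needs 46, 46/0.30 ≈ 154, both before dropout. The small downside is that PPV, NPV and overall accuracy no longer support a significance claim of their own.

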Title : Comparison of the diagnostic accuracy of Hysterosalpingo-lidocaine-foam sonography versus hysterosalpingography in tubal patency assessment to the gold standard of laparoscopy and dye testing

Date: 1/5/2022

NCT05419921

Faculty of Medicine, Cairo University Postgraduate Research Program Template

1- Study

Title :

Comparison of the diagnostic accuracy of Hysterosalpingo-lidocaine-foam sonography versus hysterosalpingography in tubal patency assessment to the gold standard of laparoscopy and dye testing

Degree: Date of registration: May 2022

2. Investigators :

1-[name] [name] & Gyn Cairo university
2-[name] Assisstant [name] & Gyn Cairo University
3-[name] Assistant Lecturer Obs & Gyn New Giza University
4-[name] Lecturer Obs & Gyn Cairo University
5-[name] Medical Student Cairo University

3. Investigators:

4. Background:

Tubal disease accounts for 30-40% of female factors of infertility.(1) Therefore, tubal testing is an essential part of female infertility work-up.(2,3) Since falsely occluded tubes may lead to unnecessary interventions and falsely patent tubes may lead to unsuccessful in-vitro fertilization embryo transfer (IVF-ET) trials,(5,6) an accurate tubal test is an essential.

laparoscopy with dye testing (LDT), i.e., laparoscopic chromopertubation, is the gold standard tubal patency test.(1,6,7) It is the recommended tubal test by the National Institute for Health and Clinical Excellence (NICE) and the European Society of Human Reproduction and Embryology (ESHRE) for women suspected to have tubal disease as it allows for direct visualization, diagnosis, and treatment of tubal and other pelvic pathologies.(3,8) However,

LDT is an invasive procedure requiring general anesthesia that can be associated with bleeding and visceral injury.(1,6,7,9)

Hysterosalpingogram (HSG) has been reported to have sensitivity of 53% and specificity of 87% in the diagnosis of tubal block.(4) It has been the most commonly used initial tubal patency test as it offers a less-invasive and less-expensive alternative to LDT.(6) However, HSG is associated with radiation exposure, pain, and allergy. It cannot diagnose myometrial or ovarian pathologies as well.(1,6,7,9)

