Women in the reproductive age group between 18- and 40-years old presenting with primary or secondary infertility who underwent HSG in the previous 5 years as a part of their infertility work-up with availability of good-quality HSG images, & did not get pregnant in this period, and gave no history of incidences that might affect their tubes, such as : abdominal surgery or laparoscopy, pelvic inflammatory disease, smoking, and intrauterine device insertion.

Women fitting these inclusion criteria and scheduled for LDT as part of their infertility work up will be considered. HyLiFoSy-PD will be carried out few days before the already scheduled LDT.

The study will be conducted in the Cairo fetal medicine unit, department of Obstetrics and gynecology, Cairo university.

Inclusion criteria:

- 1. Age group (18-40)
- 2. Informed signed Written consent.
- 3. Scheduled for LDT as a part of their infertility management

- 4. Have undergone HSG in the previous 5 years with the availability of good-quality HSG images.
- 5. No incident factors that might have affected the tubal status after she underwent HSG within the previous 5 years, such as ; abdominal surgery or laparoscopy, pelvic inflammatory disease, smoking, and intrauterine device insertion.

Exclusion criteria:

Women with any of these factors will be excluded:

- 1. LDT scheduled for a therapeutic purpose due to a known tubal or ovarian pathology
- 2. Lack of good-quality HSG images.
- 3. Withdrawal of consent.
- 4. Using contraception
- 5. Women outside reproductive age
- 6. Known allergy to lidocaine
- 7. Active pelvic inflammatory disease
- 8. Undiagnosed genital tract bleeding.
- 9. Evident tubal pathology (such as hydrosalpinx) or pregnancy diagnosed by transvaginal ultrasound (TV-US) prior to performing HyLiFoSy-PD

Methodology in details

Interpretation of HSG results:

Review of the HSG films will be done for assessment of the tubal patency; tubes will be considered patent if the dye is seen throughout their whole length and till their ends with a positive immediate spill or a spill in the delayed film. If the dye does not pass through one or both cornual ends, or if a part of the tube is seen filled with dye but not the whole length then tubal obstruction will be considered. Patients with hydrosalpinx seen by HSG are to be assessed first by US if no visible hydrosalpinx is seen by US and she has no signs of PID then she can proceed to the HyLiFoSy-PD procedure.

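### Section 10's 90% power is somewhat overstated for 100 evaluable women: 89% by its own formula, about 86% with a mid-p or asymptotic McNemar test, 80% with the exact test

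*Combined protocol and SAP*

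**What the plan says.** Section 10 (Sample size) prints a formula for comparing two sensitivities measured in the same diseased women. It gives the inputs as "With power of the study 90%, CI 95%, average sensitivity of HSG is 0.55", a sensitivity of 0.90 for HyLiFoSy-PD, and 30% prevalence of tubal pathology. It concludes that "100 patients are required to fulfill the sample size" and adds 5 women for 5% dropout, making 105.

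Three other places bear on this:

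- Section 4 (Background) cites for HSG the same reference 4 that section 10 uses, but says that HSG "has been reported to have sensitivity of 53% and specificity of 87% in the diagnosis of tubal block". Section 10 uses 0.55.
- Section 4 also cites reference 1, the source given in section 10 for the 30% prevalence, and there says: "Tubal disease accounts for 30-40% of female factors of infertility". Section 8, exclusion criterion 9, removes women with "Evident tubal pathology (such as hydrosalpinx) or pregnancy diagnosed by transvaginal ultrasound".
- Section 11 (Statistical analysis) says that "P-values less than 0.05 will be considered statistically significant". The only test it names is one-way ANOVA. No paired test is named, and the plan does not say whether the unit of analysis is the woman or the tube.

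**The concern.** The trial's objective is the difference in accuracy between the two tests, and section 10 sizes it on the difference in sensitivity. Only LDT-positive women (tubal block at laparoscopy) inform that comparison, and among them only those in whom HSG and HyLiFoSy disagree. That leaves about 14 informative women, few enough for a large-sample formula to be optimistic.

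Women are recruited before LDT, so the number who turn out LDT-positive is random. The formula treats it as fixed.

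A non-significant result would be read against a stated 10% risk of missing the planned difference. If the real risk is 14% to 20%, that reading is too confident. This is before any loss to stopped or inconclusive procedures beyond the 5% allowance.

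**Working it through.** **Inputs, all from section 10.** Se1 = 0.55 (HSG), Se2 = 0.90 (HyLiFoSy-PD), two-sided 5% (the formula uses z at 1 − α/2 = 1.960), power 90% (z = 1.2816), prevalence 0.30. All counts below are women.

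**Step 1: the plan's own formula.**

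- Λ = 0.45 × 0.90 + 0.10 × 0.55 = 0.405 + 0.055 = 0.46
- ζ = 0.405 − 0.055 = 0.35
- Λ² − ζ²(3 + Λ)/4 = 0.2116 − 0.1225 × 3.46/4 = 0.10564, with square root 0.3250
- N_disease = (1.960 × 0.46 + 1.2816 × 0.3250)² / (0.46 × 0.1225) = (0.9016 + 0.4165)² / 0.05635 = 30.83
- Women: 30.83/0.30 = 102.8, so 103. If rounded up to 31 first, 31/0.30 = 103.3, so 104.

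The stated 100 corresponds to 100 × 0.30 = 30 LDT-positive women. Inverting the formula at 30: (√(30 × 0.05635) − 0.9016)/0.3250 = (1.3002 − 0.9016)/0.3250 = 1.226, which is 89.0% power. The stated figure is therefore 3 to 4 women, or about one point of power, short on its own terms. Averaging the formula over an LDT-positive count distributed Binomial(100, 0.30) gives 87.7%.

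**Step 2: enumerated power of a paired test.** Expected discordant pairs are 30 × 0.46 = 13.8. With n LDT-positive women, the number of discordant pairs is Binomial(n, 0.46). Given that number, the pairs favouring HyLiFoSy are binomial with probability 0.405/0.46 = 0.880. Summing over all outcomes with p ≤ 0.05 gives:

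| Setting (30% prevalence) | Exact McNemar | Mid-p | Asymptotic |
|---|---|---|---|
| Exactly 30 LDT-positive | 81.0% | 87.0% | 87.0% |
| 100 evaluable, random count | 79.7% | 85.9% | 86.0% |
| 104 evaluable, random count | 81.7% | 87.4% | 87.5% |
| 105 evaluable, random count | 82.2% | 87.7% | 87.8% |
| 112 evaluable, random count | 85.2% | 89.9% | 90.0% |

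From the formula's 89%, about 2 points are lost to the large-sample approximation and 1 more to the random count. Choosing the exact test costs a further 6. At 30% prevalence, the chance that 100 women yield fewer than 31 LDT-positive is 55%. The type I error at 30 LDT-positive women is 0.026 for the exact test and 0.045 for mid-p.

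**Step 3: sensitivity to the inputs, 100 evaluable women.** Prevalences other than 30% are assumed values.

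| Prevalence | 20% | 25% | 30% | 35% | 40% |
|---|---|---|---|---|---|
| Mid-p | 66% | 78% | 86% | 91% | 95% |
| Exact | 55% | 69% | 80% | 87% | 92% |

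- HyLiFoSy sensitivity 0.85 (assumed), 30% prevalence: mid-p 70%, exact 62%.
- HSG sensitivity 0.53 (section 4): the formula gives 28.1 LDT-positive women, so 94 women, or 29/0.30 = 96.7, so 97. Formula power at 30 LDT-positive women is 92%.
- Dependence: the printed Λ and ζ assume that the two tests err independently. Keeping the 0.35 difference but setting the smaller discordant cell at 0.02 instead of 0.055 raises mid-p power to 94% (exact 90%). Setting it at 0.10 lowers exact power to 70% and asymptotic power to 77%.

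**The case against.** The strongest reply is that section 10 is nearly right. Its own formula gives 89% at 30 LDT-positive women, and 103 against 100 is a rounding-sized gap. The lower figures come from naming a McNemar test, enumerating it and letting the LDT-positive count vary, none of which the plan states. This largely stands on scale: the formula shortfall is about one point. It does not rescue the 90%, because the most favourable paired tests enumerated still reach only 86%, and the random count follows from recruiting before LDT.

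A reader might infer that the design has only 80% power. The documents do not support that as the headline. The 80% belongs to the exact McNemar test, which is conservative here and which the plan does not name.

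A reader might also infer that the 30% prevalence was misread from a share of female-factor causes, and that the true cohort prevalence is lower. The shared citation makes the first possible but does not prove it, since the source cannot be checked here. The direction is open too. Excluding evident tubal pathology could lower prevalence. Referral for laparoscopy after continued infertility could raise it, and women with hydrosalpinx on HSG but none on ultrasound may still enter. The background range is 30-40%, and the plan took its lower end.

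The remaining favourable points also stand: an HSG sensitivity of 0.53 or positive dependence between the tests would raise power. But section 10 states 0.55, and its formula assumes independence, so its 90% has to be judged on those terms.

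**Conclusion.** The point holds in a limited form. On section 10's stated inputs, 100 evaluable women do not reach 90% power by any route checked: 89% by the printed formula with the count fixed at 30, about 86% for mid-p or asymptotic McNemar, and 80% for exact McNemar. If all 105 women are evaluable, the enumerated figures are about 88% and 82%.

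These figures rest on sensitivities of 0.55 and 0.90, independence of the two tests given disease, 30% prevalence, a two-sided 5% level and the woman as the unit of analysis. The bigger uncertainty is prevalence, for which the documents give no cohort figure. Over an assumed 20% to 40%, mid-p power runs from 66% to 95%. The mismatch between the ANOVA in section 11 and a paired binary comparison is a separate matter; here it means only that the power claim is tied to no suitable test.

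**What to change.** Reword section 10 as follows:

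1. State about 86% power for 100 evaluable women with a mid-p McNemar test on LDT-positive women (80% if the exact test is used), and name the chosen test, and the woman as the unit, as what the power refers to.
2. Note that the printed formula returns 103 to 104 women for 90%. Do not present 104 as giving 90% with mid-p: it gives about 87%, and about 112 evaluable women would be needed.
3. Add a two-way table of power by prevalence (20% to 40%, labelled as assumed) and HyLiFoSy sensitivity (for example 0.80 to 0.90).
4. Say where the 30% comes from and why it should apply to this cohort, or say that it is an assumption.
5. State that positive dependence between the tests raises power, and that an HSG sensitivity of 0.53 would bring the formula to 94 to 97 women. Reconcile 0.53 with 0.55.

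This costs a paragraph and a table. No extra patients are needed to correct the statement; the only downside is a slightly less favourable stated power.

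### Section 10 enters an HSG sensitivity of 0.55 where the Background reports 53% from the same reference, and with 0.55 the printed formula needs 103–104 women, not 100 (minor)

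*Combined protocol and SAP*

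**What the plan says.** Section 4 (Background) states: "Hysterosalpingogram (HSG) has been reported to have sensitivity of 53% and specificity of 87% in the diagnosis of tubal block.(4").

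Section 10 (Sample size) prints a formula for comparing two sensitivities in the same diseased women and then lists its inputs:

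- "With power of the study 90%, CI 95"%
- "average sensitivity of HSG is 0.55,(4")
- "sensitivity of HyLiFoSy-PD is 90%,(30")
- "prevalence of tubal pathology is 30%,(1")

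It concludes that "100 patients are required to fulfill the sample size". Five women are then added for 5% dropout, for a total of 105. Neither the number of LDT-positive women nor any rounding step is shown. Section 11 (Statistical analysis) sets the 5% significance level: "P-values less than 0.05 will be considered statistically significant".

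**The concern.** Two values for the same quantity, the sensitivity of HSG for tubal block, carry the same reference number. Section 10 calls its value an average but does not say what was averaged. This is not just a slip in the introduction, because HSG sensitivity is one of the two sensitivities in the sample-size formula for the study's main comparison.

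Two things need checking: whether the stated 100 follows from the input that section 10 says it used, and how far the result moves if the Background value is used instead. At stake is whether a reader can get from the stated inputs to the stated sample size and power.

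**Working it through.** **Inputs.** HyLiFoSy-PD sensitivity Se2 = 0.90, prevalence 0.30 and power 90% come from section 10. The 5% level is two-sided, because the printed formula uses z at 1−α/2. HSG sensitivity Se1 is 0.55 (section 10) or 0.53 (section 4). The normal quantiles are 1.960 and 1.282.

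**Formula, as printed in section 10.**

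Λ = (1−Se1)Se2 + (1−Se2)Se1

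ζ = (1−Se1)Se2 − (1−Se2)Se1

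N (LDT-positive) = {1.960·Λ + 1.282·√(Λ² − ζ²(3+Λ)/4)}² / (Λζ²)

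Total women = N / 0.30.

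**Step 1: the plan's own input, Se1 = 0.55.**

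- Λ = 0.45×0.90 + 0.10×0.55 = 0.405 + 0.055 = 0.460; ζ = 0.405 − 0.055 = 0.350.
- Square-root term: √(0.2116 − 0.1225×3.46/4) = √0.1056 = 0.325.
- N = (0.9016 + 0.4165)² / (0.460×0.1225) = 1.737 / 0.05635 = 30.83.
- Total = 30.83/0.30 = 102.8, so 103 women. Rounding up to 31 positives first gives 31/0.30 = 103.3, so 104.

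The stated 100 is close to this (2.7% below 102.8), but neither rounding gives 100.

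**Step 2: the Background value, Se1 = 0.53.**

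- Λ = 0.423 + 0.053 = 0.476; ζ = 0.423 − 0.053 = 0.370.
- Square-root term: √(0.2266 − 0.1369×3.476/4) = √0.1076 = 0.328.
- N = (0.9329 + 0.4204)² / (0.476×0.1369) = 1.832 / 0.06516 = 28.11.
- Total = 28.11/0.30 = 93.7, so 94 women. Rounding up to 29 positives first gives 96.7, so 97.

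**Step 3: power with 100 women.** One hundred women at 30% prevalence give 30 expected positives. Solving the same formula for power:

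Power = Φ[(√(30·Λζ²) − 1.960·Λ) / √(Λ² − ζ²(3+Λ)/4)]

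- Se1 = 0.55: (1.3002 − 0.9016)/0.3250 = 1.226, so 89.0%.
- Se1 = 0.53: (1.3982 − 0.9329)/0.3280 = 1.418, so 92.2%.

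| HSG sensitivity | Where stated | LDT-positive women needed | Total women needed | Formula power with 100 women |
|---|---|---|---|---|
| 0.55 | Section 10 | 30.83 | 103–104 | 89.0% |
| 0.53 | Section 4 | 28.11 | 94–97 | 92.2% |

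**Step 4: what would give exactly 100?** At Se1 = 0.54 the formula gives 29.42, which rounds up to 30, and 30/0.30 = 100. That value does not appear in the plan, so this shows only that 100 lies between the two printed values. It does not show how 100 was obtained.

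**The case against.** The strongest reply is that this hardly matters. Section 10 names 0.55 in the same sentence as the 90% and the 100, and the Background makes no power claim. There is therefore one calculation with one stated HSG input. That input is the conservative one: it assumes a smaller difference between the tests and asks for more women, so moving to 53% would only improve the formula power.

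The gap is also small beside ordinary planning uncertainty. The number of LDT-positive women among 100 has a standard deviation of about √(100×0.30×0.70) = 4.6, larger than the 30.8 − 28.1 = 2.7 separating the two requirements. A prevalence of 31% instead of 30% would bring the requirement at 0.55 to 30.83/0.31 = 99.5. Finally, the reference is a review that may contain more than one estimate for HSG, so an average of 0.55 and a reported 53% could both be faithful to it.

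Most of this stands. A reader might infer that one cannot tell which input the 90% rests on, but section 10 says that it is 0.55. A reader might also infer that the choice between 53% and 55% decides whether the power claim is supported. Formula power moves only from 89% to 92%, which is too narrow a range for that. Nor do the documents show that 0.55 is wrong or that the Background must change, since the source cannot be checked from them.

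What the reply does not remove is the arithmetic. Conservatism might explain choosing 0.55, but not stopping at 100 when that input needs 103–104. The five extra women do not close the gap either, because section 10 assigns them to dropout.

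**Conclusion.** The point holds as a minor one. The plan gives two HSG sensitivities from one reference without explaining the difference, and its stated sample size does not follow exactly from the value it uses. The shortfall at 0.55 is three or four women, or about one percentage point of formula power (89.0% against 90%). At 0.53 there is a surplus of three to six women and power of about 92%.

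These figures rest on the plan's own formula. Its Λ and ζ treat the two tests' errors as independent given LDT status, and the conversion to total women assumes that exactly 30% are LDT-positive.

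A reader might infer that the study is underpowered. The 53%/0.55 discrepancy does not support that. An exact two-sided McNemar calculation at 30 positives does give lower power, about 81% at 0.55 and 85% at 0.53. That reflects the approximation in the formula, which is a separate question from the choice of HSG input.

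**What to change.** Reconcile the two HSG values in one of two ways:

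- use a single value, traceable to the reference, in both section 4 and section 10; or
- keep 0.55 in section 10 and add one clause saying how it was derived. The 53% may then stay in the Background as a reported figure.

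In section 10, show the number of LDT-positive women and how it was rounded. Then restate one of the following for the value chosen:

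- the power that 100 evaluable women give by the plan's formula: about 89% at 0.55, or 92% at 0.53; or
- the number of evaluable women required before dropout: 103–104 at 0.55, or 94–97 at 0.53.

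This costs one reconciled figure and one rewritten sentence. No extra women need be enrolled if the power is restated. The only downside is a slightly less favourable stated power if 0.55 is kept.
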